Investigational Product: Form: Composition:	
High-Dose Quadrivalent Influenza Vaccine, (Zonal Purified, Split Virus) 2020-2021 Strains (QIV-HD), provided in a pre-filled single-dose syringe
 
Suspension
 
Each 0.7 mL dose of QIV-HD will contain:
 
Strains to be determined based on World Health Organization (WHO) / the United States Vaccines and Related Biological Products Advisory Committee (VRBPAC) recommendations for the 2020-2021 NH influenza season.
 
Active Substances:
 
 • A/Guangdong-Maonan/SWL1536/2019 CNIC-1909 (H1N1) strain 60 µg hemagglutinin (HA) • A/Hong Kong/2671/2019 IVR-208 (H3N2) strain 60 µg HA • B/Washington/02/2019 wt virus strain 60 µg HA • B/Phuket/3073/2013 wt virus strain 60 µg HA 
Excipients:
 
 • Buffered saline solution quantity sufficient (qs) to appropriate volume • Octylphenol Ethoxylate (Triton X-100®) not more than 350 µg 
Preservative is not used in the manufacture of QIV-HD.

Route: Batch Number:	
IM, injected into the upper arm (deltoid area)
 
TBD

Control Product: Form: Composition:	
████████ (Influenza HA Vaccine, █████)
 
Local Standard-Dose Inactivated Quadrivalent Influenza Vaccine, 2020-2021 Strains (QIV-SD), provided in a pre-filled single-dose syringe
 
Suspension
 
Each 0.5 mL dose of QIV-SD will contain:
 
Strains to be determined by Ministry of Health, Labour and Welfare (MHLW) for the 2020-2021 NH influenza season.

	
Active substances:
 
 • A/(H1N1)-like strain 15 µg HA • A/(H3N2)-like strain 15 µg HA • B/(Victoria lineage)-like strain 15 µg HA • B/(Yamagata lineage)-like strain 15 µg HA 
Excipients:
 
Buffered saline solution qs to appropriate volume

Route:	SC, injected into the upper arm (posterior region)
Batch Number:	TBD
Inclusion Criteria:	
An individual must fulfill all of the following criteria to be eligible for study enrollment:
 
I 01. Aged ≥60 years on the day of inclusion
 
I 02. Informed consent form has been signed and dated
 
I 03. Able to attend all scheduled visits and to comply with all study procedures

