1.3.2 Potential Risks to Subjects

As with any vaccine, it is important to note that vaccination with QIV-HD may not protect all recipients against the disease it is designed to prevent (i.e., influenza). See below for other potential risks.

Possible Reactions to Blood Draw

Venipuncture causes transient discomfort and may cause temporary hypotension from a vasovagal response (e.g., fainting). If pressure is not applied long enough to the venipuncture site, bruising

due to bleeding beneath the skin may occur. Infection at the site of needle insertion could theoretically occur but is exceedingly rare when the standard sterile technique is utilized.

Possible Reactions to Vaccination

Vaccine injection into the deltoid muscle causes transient discomfort. Immediate and potentially life-threatening allergic reactions to the vaccine could be manifested by adverse events (AEs) such as laryngeal edema, asthma, or hypotension. These types of reactions are exceedingly rare and would most likely occur in persons with a severe reaction to influenza vaccine in the past.

The rate of injection site reactions is expected to be higher with the SC route compared to the IM route due to the fact that the inflammatory reactions induced by the vaccines are closer to the surface of the skin and therefore more visible to direct examination.

Post-marketing Experience with TIV-HD (Fluzone High Dose)

The following events have been spontaneously reported during the post-approval use of TIV-HD. These events are reported voluntarily from a population of uncertain size, consequently it is not always possible to reliably estimate the frequency of the events or establish a causal relationship to vaccine exposure. AEs were included based on one or more of the following factors: intensity, frequency of reporting, or strength of evidence for a causal relationship to TIV-HD.

Events reported spontaneously during post-approval use of TIV-HD and may occur in subjects receiving QIV-HD are:

- Blood and Lymphatic System Disorders: thrombocytopenia, lymphadenopathy
- Immune System Disorders: anaphylaxis, other allergic/hypersensitivity reactions (including angioedema)
- Eye Disorders: ocular hyperemia
- Nervous System Disorders: Guillain-Barré syndrome, convulsions, febrile convulsions, myelitis (including encephalomyelitis and transverse myelitis), facial palsy (Bell's palsy), optic neuritis/neuropathy, brachial neuritis, syncope (shortly after vaccination), paresthesia

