5.1.2 Justification of the Study Design

The objectives of QHD00010-EFC15150 will be to assess the immunogenicity (as assessed by HAI GMTs and seroconversion rates at 28 days post-vaccination) and safety of QIV-HD administered by IM route compared with the local QIV-SD administered by SC route.

The control product is the local QIV-SD because it is the only seasonal influenza vaccine licensed in Japan.

Given the different volumes and administration routes of the QIV-HD and the local QIV-SD vaccines, QHD00010-EFC15150 will be a modified double-blind study in which only designated study staff at each study site will know which vaccine has been administered to the subjects. The subjects and the Investigator/Sub-investigator in charge of the safety assessment will be blinded in order to decrease the potential bias in safety assessment.

The risk / benefit ratio is appropriate for the conduct of a Phase III clinical study with QIV-HD without an early safety data review for the following reasons:

- There were no safety issues identified from the Phase I/II study (QHD00008-DFI15130) which enrolled 175 Japanese adults 65 years of age and older, and evaluated the QIV-HD formulation administered by SC route or IM route compared with the local QIV-SD administered by SC route.
- There were no safety issues identified from the Phase III (QHD00013) US study which enrolled 2670 adults, 65 years and older, and evaluated the QIV-HD formulation administered by IM route compared with the licensed TIV-HD also administered by IM route. This study successfully supported the licensure of QIV-HD in the US in November 2019. In April 2020, QIV-HD also received a positive opinion from the European Union health authority with marketing authorizations granted by Norway, France, and Latvia as of 21 April 2020.
- The QIV-HD vaccine assessed in QHD00010-EFC15150 is manufactured using the same drug substance manufacturing process as the currently licensed TIV-HD manufacturing process.
- There is a large vaccine safety database generated following significant post-marketing use of TIV-HD (more than 137 million doses distributed since 2009).

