12. Administer the corresponding vaccine to the subject intramuscularly or subcutaneously into the upper arm (intramuscularly into the deltoid area or subcutaneously into the posterior region).

Note: The vaccine is prepared by an unblinded study staff (a designated administrator such as an Investigator/Sub-investigator, a nurse, or a designated pharmacist) and administered by the unblinded administrator (a designated study staff such as an Investigator/Sub-investigator or nurse) without the presence of any other study staff who may be an assessor for safety in subsequent visits. The subjects are also blinded with an eye mask or other appropriate methods during vaccine administration. The vaccine must be administered on the side opposite to that of the blood sampling.

Note: The administrator records the injection side / dose number in the CRB and the injection site / route in the administration record. The detachable corresponding label is affixed in the administration record.

13. Keep the subject under medical surveillance for at least 30 minutes after the injection and report the occurrence or non-occurrence of any AE in the CRB.
14. Provide the subject with a diary card to record any solicited reactions and AEs, together with instructions for its completion, including explanations on the definition and use of intensity scales for collection of AEs.
15. Provide the subject with a ruler to measure the size of any injection site reaction, a thermometer for temperature measurement², and instructions on how to use them.
16. Remind the subject to bring the diary card on V02.
17. Instruct on the need to promptly report any SAE and AESI that may occur at any time during the study.
18. Complete the relevant (electronic) case report forms (CRFs) for this visit.

Day 8 Telephone Call (8 days [+ 2 days] after Visit 1)

Note: If Day 8 Telephone Call falls on a weekend or a holiday, the telephone call may be made on the following business day.

² Tympanic and temporal artery thermometers should not be used.

1. Record relevant information concerning the subject's health status on the telephone contact form. If an SAE occurred, follow the instructions in [Section 10.1](#) for reporting it.
2. Remind the subject to do the following:
 - Complete the D0–D7 pages of the diary card.
 - Complete the remaining pages of the diary card, and bring them to V02.
 - Notify the site in case of an SAE and/or an AESI.

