6.4 BLINDING AND CODE-BREAKING PROCEDURES

To ensure that objective data are obtained, the study is designed as a modified double-blind study as follows:

- The Investigator/Sub-investigator in charge of the safety assessment and the study staff who collect the safety data will not know which vaccine was administered or the route of administration.
- The unblinded administrator, who is a designated study staff (e.g., an Investigator/Sub-investigator or a nurse), will administer the vaccine. The unblinded administrator needs to keep himself/herself blinded until the key code is released from the sponsor, even after the database lock for the CRB.
- The subjects will be blinded with an eye mask or other appropriate methods during administration.
- The laboratory personnel who analyze the blood sample will not know which vaccine was administered.

The Investigator/Sub-investigator in charge of the safety assessment will not be present during the vaccination but will be available on site in case of emergency (e.g., anaphylactic shock).

Dose number will be used to identify each vaccine for the purpose of randomization, vaccination, and the recording of vaccine administered. Dose numbers will be randomly assigned to QIV-HD and QIV-SD. The IRT vendor will be responsible for providing the treatment group identification and dose number to be received by the enrolled subject. The subject, the Investigator, and study staff who collect the safety data and laboratory personnel who analyze the blood samples will all be blinded to the group assignment. The individual responsible for preparing/administering vaccine will not be authorized to collect any safety/serology data.

The code may be broken in the event of an AE only when the identification of the vaccine received could influence the treatment of the subject. Code-breaking should be limited to the subject(s) experiencing the AE.

The blind can be broken by the Investigator or a delegate through the IRT system, as explained in the code-breaking procedures described in the IRT operation manuals. Once the emergency has been addressed by the site, the Investigator or a delegate must notify the Sponsor if a subject's code was broken. All contact attempts with the Sponsor prior to unblinding are to be documented in the source documents, and the code breaking CRF is to be completed.

A request for the code to be broken may also be made:

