9.2.2.3.2 Reactogenicity (Solicited Reactions From Day 0 to Day 7 After Vaccination)

After vaccination, subjects will be provided with a diary card, a digital thermometer, and a flexible ruler, and will be instructed how to use them. The following items will be recorded by the subjects in the diary card on the day of vaccination and for the next 7 days (i.e., D0 through D7) until resolution:

- Daily temperature, with the route by which it was taken
- Daily measurement or intensity grade of all other solicited injection site and systemic reactions
- Action taken for each event (e.g., medication)

The action(s) taken by the subject to treat and/or manage any solicited reactions will be classified in the CRB using the following list (all applicable items should be checked):

- None
- Medication
- Health care provider contact
- Hospitalized

Subjects will be contacted by telephone 8 days (+2 days) after vaccination to remind them to record all safety information in the diary card.

If the timing of the telephone call should fall on a weekend or a holiday, the call should be made on the next business day. If contact is not made on the designated day, site staff will continue

calling until contact is made. Every telephone attempt and its outcome will be documented in the source document.

Table 1 and **Table 2** present, respectively, the injection site reactions and systemic reactions that are prelisted in the diary cards and CRB, together with the intensity scales.

Table 1 - Solicited Injection Site Reactions: Terminology, Definitions, and Intensity Scales

CRB term (MedDRA lowest level term [LLT])	Injection site pain	Injection site erythema	Injection site swelling	Injection site induration	Injection site bruising
Diary card term	Pain	Redness	Swelling	Hardening	Bruising

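### Subjects are stated to be blinded for the safety assessment, but their blind is protected only during the injection, and they then inspect a group-specific injection site while self-grading five reactions

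*Protocol*

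**What the plan says.** The synopsis gives the QIV-HD route as "IM, injected into the upper arm (deltoid area" and the control route as "SC, injected into the upper arm (posterior region". Protocol 5.1.4 (Visit 1, step 12), 6.1.1.2 and 6.1.2.2 repeat this pairing.

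On blinding, Protocol 5.1.2 describes a modified double-blind study "in which only designated study staff at each study site will know which vaccine has been administered", and adds: "The subjects and the Investigator/Sub-investigator in charge of the safety assessment will be blinded in order to decrease the potential bias in safety assessment". Section 6.4 also lists the subject among those blinded to group assignment. It says that the safety assessor and the staff who collect safety data will know neither the vaccine nor the route.

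The measure that is meant to achieve this for subjects is in 6.4: "The subjects will be blinded with an eye mask or other appropriate methods during administration". Sections 5.1.4 and 6.1.1.2 have the same limit.

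After the injection, 5.1.4 tells staff: "Provide the subject with a ruler to measure the size of any injection site reaction". Under 9.2.2.3.2 subjects keep the diary "on the day of vaccination and for the next 7 days (i.e., D0 through D7".

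**The concern.** The stated property and the described procedure do not match. Each vaccine always goes into its own area of the upper arm, and nothing is done to mask the location once the injection is over. The person said to be blinded is then asked to look at that location, with a ruler, for a week, and is also the rater of the most subjective safety items.

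Two things are at stake. First, comparisons between groups of self-graded reactions would be read as coming from blinded raters when that is not assured. Second, the location is something a subject can mention at the D8 call or at V02, and it would tell the assessor the route that 6.4 says the assessor must not know. The assessor also judges the causality of unsolicited systemic AEs (9.2.2.3.5). No item in the protocol or SAP would show whether either has happened.

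**Working it through.** The plan gives no figure on this point, so the check sets its passages side by side.

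**1. Does location identify the group?** Yes. QIV-HD always goes into the deltoid area and QIV-SD always into the posterior upper arm. No shared site or sham injection is described.

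**2. Does the plan treat site and route as unblinding?** Yes. In 5.1.4 (Visit 1, step 12) the administrator enters side and dose number in the CRB, but site and route only in the administration record. Section 6.4 names the route as something the assessor must not learn.

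**3. How long does the subject's masking last?** Only while the vaccine is given. The alternative to the eye mask is not defined, but it carries the same time limit.

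**4. How long does the subject observe the site?** D0 to D7 inclusive: 7 − 0 + 1 = 8 diary days.

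**5. Which solicited reactions does the subject grade?** There are ten (Tables 1 and 2 of the protocol).

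| Recorded by the subject as | Reactions | Count |
|---|---|---|
| Grade 1 to 3 | pain, headache, malaise, myalgia, shivering | 5 |
| Size, graded at analysis | erythema, swelling, induration, bruising | 4 |
| Temperature, graded at analysis | fever | 1 |

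The footnote to Table 1 says this explicitly for redness and swelling. SAP 5.4.2.1 treats induration and bruising in the same way. The footnote to Table 2 covers fever.

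**6. Can the location reach the assessor?** Staff speak with the subject at the D8 call and review the diary at V02 (5.1.4), and interview the subject about its content (11.1). None of these places asks the subject to withhold the location.

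**7. What is the scale?** The documents give no expected reaction rates and no size of reporting bias. For orientation only, the random error of a between-group difference at 1050 per group, with an assumed common rate p, has a 95% half-width of 1.96 × √(2p(1−p)/1050):

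- p = 0.10: 2.6 percentage points
- p = 0.30: 3.9 percentage points
- p = 0.50: 4.3 percentage points

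These figures describe precision and do not estimate bias. The SAP does not plan this interval; it plans Clopper-Pearson intervals for single proportions (4.7).

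**8. Are the primary endpoints touched?** No. Under 6.4 the laboratory staff who analyse the samples do not know the vaccine.

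**The case against.** The strongest reply is that the limit is already disclosed. The design is called modified double-blind, 5.1.2 gives different volumes and routes as the reason, and three sections say that the masking applies during administration. This stands only in part. As 5.1.2 uses the label, only designated staff know the vaccine, and subjects remain on the blinded side. The visible site after injection is never mentioned.

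A second reply is that actual unblinding needs a further step: the subject must connect a place on the arm with a vaccine. That stands. The consent text is not available, and the study title pairs each vaccine with a route, not with a site. A reader might infer that all 2100 subjects are unblinded, and the documents do not show that.

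A third reply is that the data concerned are secondary and descriptive, with no testing (Protocol 12.1.2.1, SAP 4.7), that half of the solicited reactions are measured, and that investigator assessment of solicited reactions is mandatory (9.2.2.1). This limits the weight of the point but does not remove it. Safety is a stated secondary objective, and Protocol 1.4 itself draws on a comparison of safety profiles with the control vaccine in the earlier Japanese study.

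A reader might also infer a reporting bias of a few points in a known direction from 1.3.2, which says "The rate of injection site reactions is expected to be higher with the SC route compared to the IM route". That sentence concerns injection-site reactions only, attributes the difference to visibility, and says nothing about headache, malaise, myalgia or shivering. Nor do the documents show that subjects are told it. What it does imply is that, for pain, a reporting effect could not be separated from a true route effect.

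Finally, a reader might infer that assessors see the site themselves. The documents keep the assessor away from the vaccination. The V02 examination is optional and comes at D28 or later, and nothing indicates that the site would still be recognisable. The supported path to the assessor is what the subject says.

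**Conclusion.** The statement on subject blinding is wrong as written: the procedures protect the subject's blind during the injection and not afterwards. The exposure covers five of the ten solicited reactions over 8 diary days, and, through disclosure by the subject, possibly the assessor's blind to route. The four measured site reactions and temperature are less exposed.

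The size and direction of any bias cannot be derived from the documents. That any subject infers the group rests on one assumption, namely that the subject links site or route to vaccine. Any inference that the superiority conclusion is at risk would be unfounded, because the HAI titers are read by a blinded laboratory. The point concerns secondary, descriptive safety data and how they are presented.

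**What to change.** Leave injection sites and routes as they are.

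1. In the synopsis, 5.1.2 and 6.4, state that subjects are masked during administration only and that their blind is not assured afterwards, while the safety assessor, the safety-data staff and the laboratory remain blinded.
2. In 5.1.4 (Visit 1, the D8 call and Visit 2), instruct subjects not to tell safety staff where on the arm they were injected, except when this is needed for care of a reaction.
3. In SAP 4.7.2, state that between-group comparisons of pain, headache, malaise, myalgia and shivering are interpreted as reports from subjects who could know their group, separately from the measured reactions. The tables by named reaction are already planned, so this adds interpretation and no new output.

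An opaque dressing for the 30-minute observation is not recommended: it would not affect self-inspection from D0 to D7, and it could hide immediate site reactions that must be recorded. A treatment-guess item at V02 is optional and not needed; by then the guess would be mixed with the reactions experienced.

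The cost is a few sentences and a slightly more modest reactogenicity claim. Timing matters for item 2: inclusion was planned to end on 15 December 2020, and the SAP is dated 08 January 2021. If enrolment and follow-up are over, items 1 and 3 can still be made in the SAP and the study report.

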1 INTRODUCTION

1.1 BACKGROUND

This study will evaluate the immunogenicity and safety of high-dose quadrivalent influenza vaccine (hereafter referred to as QIV-HD) administered by intramuscular (IM) route in subjects 60 years of age and older.

Influenza is a highly contagious, acute viral respiratory disease caused by influenza type A and type B viruses. Typically characterized by the rapid onset of fever, myalgia, sore throat, and non-productive cough, influenza can also cause severe malaise lasting for several days. Individuals in high-risk groups (e.g., adults 65 years of age and older and persons with underlying medical conditions) are at high risk of influenza and its complications including primary viral pneumonia, secondary bacterial pneumonia, and/or exacerbation of underlying medical conditions such as chronic obstructive pulmonary disease and congestive heart failure (1) (2).

Vaccination remains the most effective means of preventing influenza and the complications associated with the disease. The World Health Organization (WHO) and the Advisory Committee on Immunization Practices (ACIP) in the United States (US) recommends annual vaccination against influenza because it has been shown to be effective in reducing influenza-associated morbidity and mortality (1) (3). Routine influenza vaccination for adults 65 years of age and older and adults 60 to 64 years of age with respiratory, cardiac, renal disease, or human immunodeficiency virus (HIV) has also been recommended in Japan since 2001 under the Preventative Vaccination Law (4).

The immune response to standard-dose (SD) influenza vaccines (15 micrograms [μ g] hemagglutinin [HA] per strain) is sub-optimal in adults 65 years of age and older compared to healthy young adults (5). A strategy to improve protection against influenza in adults 65 years of age and older is to increase the antigen dose (6). Sanofi Pasteur has developed a quadrivalent influenza vaccine high-dose (QIV-HD) containing 60 μ g of HA of each of 4 virus strains (A/H1N1, A/H3N2, and 1 B strain from each of the Victoria and the Yamagata lineages).

QIV-HD has been developed based on the experience gained with Sanofi Pasteur's trivalent influenza vaccine high-dose (TIV-HD) which contains 60 μ g of HA of each of 3 virus strains and is manufactured in the United States (US). TIV-HD was licensed by Sanofi Pasteur under the name Fluzone® High Dose for use in adults 65 years of age and older in the US in 2009 (7), Canada in 2015 (8), Australia in 2017 (9), Brazil in 2018, and the United Kingdom in 2019.

TIV-HD generated superior immune responses (10) (study FIM05) and improved vaccine efficacy (VE) (11) (study FIM12) compared to a trivalent influenza vaccine standard-dose (TIV-SD) in clinical studies conducted in adults 65 years of age and older. FIM12 was a large-scale, multi-center efficacy trial which demonstrated that TIV-HD was 24.2% (95% confidence interval [CI], 9.7 to 36.5) more effective in preventing laboratory-confirmed influenza illness against any

circulating strain compared to TIV-SD, or in other words, one in 4 breakthrough cases of influenza could be prevented if TIV-HD was used instead of TIV-SD in this population.

Several retrospective studies, in over 8 influenza seasons and in more than 24 million individuals 65 years of age and older, confirmed the superior protection offered by TIV-HD compared to TIV-SD against complications of influenza such as pneumonia and influenza hospitalization (13.4% [95% CI, 7.3% to 19.2%, $p<0.001$]), cardio-respiratory hospitalizations (17.9% [95% CI, 14.9% to 20.9%, $p<0.001$]) and all-cause hospitalization (8.1% [95% CI, 5.9% to 10.3%, $p<0.001$]); although the impact may vary per season (12) (13) (14) (15) (16) (17) (18) (19) (20) (21).

Based on approximately 26 500 subjects who were exposed to TIV-HD through its clinical development program or in post-marketing surveillance (ie, more than 137 million doses distributed), the safety profile of TIV-HD in humans has been shown to be well tolerated with no safety concerns.

QIV-HD is produced using the same drug substance (DS) and drug product (DP) manufacturing processes as TIV-HD except for the DP formulation step, which includes the addition of a second influenza B strain at the same HA content as the other 3 strains (60 μ g HA/strain/dose). This results in a slightly higher fill volume to provide a delivered dose of 0.7 mL.

In November 2019, QIV-HD was licensed in adults 65 years of age and older in the US. In April 2020, QIV-HD also received a positive opinion from the European Union health authority with marketing authorizations granted by Norway, France, and Latvia as of 21 April 2020. Moreover, QIV-HD has been submitted for licensure in adults 65 years of age and older in Canada (July 2019), Australia (July 2019), South Korea (January 2020), and Switzerland (March 2020).

Thus, the goal of the QIV-HD project is to also license QIV-HD for adults 60 years of age and older in Japan.

